### ***Data collection***

Study data will be collected using a bespoke portal on REDCap (Research Electronic Data Capture, Vanderbilt University, USA) at predefined time points, aligned with the clinical care pathway. An option for in-person, postal, and telephone collection will also be available to participants at each time point. (Table 1)

At the pre-operative baseline visit, participants will complete the PROMs questionnaires (FJS, OKS, EQ-5D-5L, satisfaction scores, and pain score). Pre-operative bilateral hip-knee-ankle (HKA) radiographs will be obtained to assess coronal alignment, joint line obliquity, and enable CPAK classification. For participants enrolled in the motion analysis laboratory (MAL) sub-study, a baseline assessment will be conducted during the same hospital visit.

During surgery, data will be collected relating to surgical workflow and efficiency (including case time, tourniquet time, operating room preparation and turnaround times). For the raTKA group, VELYS-acquired intra-operative data will be collected. Data from inpatient medical records will be collected. Routine postoperative radiographs will be taken in line with standard clinical practice.

At six weeks post-operatively, participants will complete the PROMs questionnaires. In addition, participants will complete a health service resource use questionnaire, which will capture clinical service contacts (including frequency and reason) and analgesic use during the follow-up period.

At six months post-operatively, participants will complete the FJS (primary outcome), and secondary PROMs questionnaires, and post-operative bilateral HKA radiographs will be obtained to assess implant positioning and limb alignment. A further health service resource use questionnaire will also be completed. MAL sub-study participants will undergo a repeat assessment.

At 12 months post-operatively, participants will complete the full set of PROMs, along with a final health service resource use questionnaire.

### ***Data management***

All study data will be recorded using case report forms (CRFs) and entered into the secure, password-protected REDCap platform. Access will be restricted to authorised members of the trial team and sponsor representatives. Personal identifiers will be replaced with coded participant IDs to ensure data confidentiality. De-identified data will be used for all statistical analyses. Data will be managed in accordance with the UK Caldicott principles, and data will be retained in excess of the minimum

eight years in accordance with sponsor policy and UK regulatory requirements. Data quality will be safeguarded through range checks, source data verification, and ongoing data monitoring by the trial team. Audits may be conducted by the Sponsor in line with routine NHS research governance.

### ***Statistical analysis***

All analyses will adhere to CONSORT reporting standards. A detailed statistical analysis plan will be finalised with the Trial Steering Committee before any formal analyses are undertaken. Baseline characteristics will be summarised to assess comparability between treatment groups. Simple descriptive statistics will follow standard conventions, including means and standard deviations or medians and interquartile ranges as appropriate for continuous variables, and counts and percentages for categorical data.

The primary analysis will examine differences between the two intervention groups (using an intention-to-treat approach) with regard to their change in FJS (preoperatively versus 6 months post-surgery). A Student's independent t-test will be used to compare mean scores between groups. Assumptions of normality and equality of variances will be assessed using diagnostic plots and Levene's test. If variances are unequal, the Welch's t-test will be applied. The results will be reported as mean differences with 95% confidence intervals and p-values.

Secondary outcomes will be analysed similarly, appropriate to the type and distribution of the data. Categorical outcomes, such as patient satisfaction and complication rates, will be compared between groups using the chi-square test. If any expected cell count is less than five, Fisher's exact test will be applied. Effect sizes will be reported alongside these comparisons using risk ratios or odds ratios with 95% confidence intervals to provide a measure of the magnitude and precision of differences between groups.

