### ***Sample size***

The sample size calculation is based on detecting a minimum clinically important difference (MCID) of 7 points in the FJS at six months post-operatively. This is informed by Alton et al (2025), and a standard deviation of 24 points, as reported in Clement et al., 2021. Using a one-sided alpha of 0.05 and a power of 80%, it was calculated that 147 participants per group would be required. To account for an anticipated 15% loss to follow-up, the final recruitment target is 173 participants per group, yielding a total study population of 346 participants.

Outcome data from the internal pilot (the first 100 study participants who have completed their 6-month follow-up) will be analysed. A blinded pooled estimate of the outcome variance will be computed and used in a pre-specified sample size re-estimation algorithm. The analysis team will remain blinded to treatment allocation; any sample size adjustments will be made according to the pre-specified rules to preserve type I error.

For the motion analysis sub-study, a sample size of 52 participants (26 in the raTKA and mTKA groups respectively) has been determined to provide sufficient power to detect expected differences in peak medial knee contact force compared with matched healthy controls.

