### ***Outcomes***

The primary outcome will be the change in Forgotten Joint Score (FJS) at two timepoints, preoperatively versus 6 months post-surgery. Secondary outcome measures will include PROMs; clinical outcomes; functional, physiological, and technology-enabled activity measures; health service and economic outcomes; technical surgical/radiographic measures, and biomechanical outcomes using motion analysis laboratory assessment. A dedicated motion analysis laboratory (MAL) study will be conducted as a nested sub-study. (Figure 2)

Outcomes	
Primary measure	Change in FJS [pre-surgery, 6 months] 
Secondary Measures	Change in FJS [pre-surgery, 6 weeks, 12 months] Absolute FJS [6 weeks, 6 months, 12 months] OKS [pre-operative, 6 weeks, 6 months, 12 months]  EQ-5D-5L [pre-operative, 6 weeks, 6 months, and 12 months]  Satisfaction Score (NRS, Likert scale) [6 weeks, 6 months, 12 months]  Pain score (VAS) [6 weeks, 6 months, 12 months]  PROM anchor questions  Functional, physiological and technology-enabled activity measures Change in radiographic parameters Alignment measures (HKA, JLO, CPAK, component size and position)  Surgical time (preparation, case, tourniquet & turnaround) NASA TLX & clinician experience (after 1st and every 5th case)  Health service resource utilisation (clinical contacts, analgesic use)

**Fig 2.** Primary and secondary outcome measures. Time points are relative to date of surgery.

FJS: Forgotten Joint Score, OKS: Oxford Knee Score, EQ-5D-5L; EuroQol EQ-5D 5-Level, NRS: numeric rating scale, VAS: visual analogue scale, HKA: hip-knee-ankle axis, JLO: joint line obliquity, CPAK: coronal plane alignment of the knee, NASA TLX: NASA Task Load Index.

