### ***Handling of missing data***

Missing data will be carefully evaluated, and reasons for missingness recorded wherever possible. Where appropriate, multiple imputation will be used, and analyses of imputed datasets will be presented alongside sensitivity analyses tailored to the type of missing data.

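### The named primary t-test uses only the pre-operative and six-month FJS, and the conditional imputation wording does not secure the intention-to-treat label

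*Protocol*

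**What the plan says.** The Statistical analysis section of the protocol sets out its main comparison as "differences between the two intervention groups (using an intention-to-treat approach) with regard to their change in FJS (preoperatively versus 6 months post-surgery". It names the method: "A Student's independent t-test will be used to compare mean scores between groups", with Welch's version if variances differ. No other visit enters that comparison.

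FJS is collected more often than this. The outcome table lists as secondary "Change in FJS [pre-surgery, 6 weeks, 12 months", and the Data collection section and Table 1 schedule patient-reported outcomes before surgery and at 6 weeks, 6 months and 12 months. For these other outcomes, "Secondary outcomes will be analysed similarly, appropriate to the type and distribution of the data".

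The Sample size section inflates the target "To account for an anticipated 15% loss to follow-up", from 147 to 173 per group.

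On missing data the protocol says: "Where appropriate, multiple imputation will be used". It adds that results from imputed datasets will appear next to sensitivity analyses. It does not say which result is primary, or which variables enter the imputation model.

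**The concern.** A two-sample t-test on change needs one pre-operative and one six-month score per person. Without imputation, anyone lacking the six-month FJS contributes nothing, even if other post-operative scores exist. An intention-to-treat claim covers all randomised participants, so the plan should say how those without the six-month score are represented. The protocol names a test that cannot represent them and adds a conditional imputation clause, so two different results could each be called the primary intention-to-treat result.

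The choice matters if participants who recover poorly early on are more likely to be lost, and more so in one arm than the other. The observed-case difference is then biased. An analysis that uses the 6-week and 12-month FJS is valid under the weaker assumption that dropout depends on scores already observed.

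**Working it through.** **1. The plan's own figure.** Inputs from the Sample size section: difference 7, SD 24, one-sided alpha 0.05, power 80%.

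- Normal approximation: n = 2 × (1.645 + 0.842)² × (24/7)² = 2 × 6.185 × 11.755 = 145.4, so 146 per group.
- t-test solution: 146.03, rounded up to 147.
- Inflation: 147 / 0.85 = 172.9, so 173 per group and 346 in total.

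The stated 147, 173 and 346 are reproduced.

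**2. How many six-month scores may be missing.** 0.15 × 346 = 51.9, and 346 − 2 × 147 = 52. The internal-pilot retention thresholds give a range around this. At 90% (the lower limit of Go), 0.10 × 346 ≈ 35 are missing. At 75% (the lower limit of Amend), 0.25 × 346 ≈ 87 are missing.

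**3. Power at stake.** With 147 observed per arm, 7 / (24 × √(2/147)) = 2.50, and 2.50 − 1.645 = 0.856, which gives 80.4% one-sided power. The planned loss therefore does not take the observed-case test below its target.

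For the gain from the other visits, let f be the share of the 26 missing per arm (173 − 147) who have another post-operative FJS, and R² the variance of the six-month score that it explains. The protocol gives neither, so both are assumptions. Effective n per arm = 1 / ((1 − R²)/147 + R²/(147 + 26f)).

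| f | R² | Effective n per arm | One-sided power |
|---|---|---|---|
| 0 | any | 147 | 80.4% |
| 0.5 | 0.25 | 150.0 | 81.1% |
| 0.5 | 0.64 | 155.1 | 82.2% |
| 1 | 0.25 | 152.7 | 81.7% |
| 1 | 0.64 | 162.6 | 83.8% |
| All 173 observed | – | 173 | 85.7% |

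The gain is about 1 to 3 percentage points.

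**4. Bias at stake.** If a share m is missing in each arm, the observed mean exceeds the full-arm mean by m × (observed mean − missing mean). The bias in the between-arm difference is m times the amount by which this gap differs between arms. With m = 0.15, gaps that differ by 5, 7 or 10 points give 0.75, 1.05 or 1.5 points. Equal gaps give zero.

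Simulations used 173 per arm, a true difference of 7, about 15% missing at six months (up to 18% in some runs), SDs of 17, 22, 24 and 24 at the four visits, and correlations of 0.55 (6 weeks with 6 months) and 0.70 (6 with 12 months). Only the 24 at six months is the protocol's figure. The rest, including the dropout models, are assumptions. There were 300 to 600 runs per scenario, with simulation error of about 0.12 to 0.15 where recorded.

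| Dropout driven by low 6-week FJS | Observed-case bias (points) |
|---|---|
| Same pattern in both arms | −0.06 |
| One arm only | 0.7 to 1.1 |
| Opposite patterns by arm | 1.5 to 2.0 (2.8 if the dependence is strong) |
| Nobody missing at 6 months returns at 12 months | 1.2 (one arm), 2.6 (opposite) |

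In these scenarios the likelihood-based repeated-measures estimate stayed within about 0.25 of the truth. It stayed within 0.1 in the last row, where only the 6-week score was available to help. With dropout unrelated to outcome, the standard error fell from 2.82 to 2.71, about 4%.

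**The case against.** The strongest reply is that the protocol already provides for multiple imputation, that a t-test can be run on imputed datasets, and that the content of the imputation model normally belongs in the statistical analysis plan, which is not shown. Imputation that includes the 6-week and 12-month FJS rests on the same assumption as a repeated-measures model. Much of this stands. A reader might infer that the protocol makes a complete-case t-test primary and drops 52 people. It does not: imputed analyses are to be presented with sensitivity analyses, and no complete-case analysis is named as primary. What remains is that the protocol itself fixes the primary test and its label, while the only text that could reconcile them is conditional and silent on which result leads.

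A reader might also infer that all of the roughly 52 would have 6-week and 12-month scores in hand. The 52 is a loss-to-follow-up allowance, and the protocol gives no count of those with other scores. Some lost participants would lack a 12-month score too. The simulation without 12-month returners suggests that this does not remove the benefit, provided the 6-week score exists.

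Finally, differential dropout is not shown to be likely. Participants are blinded, several routes of data collection and reminders are planned, and the minimum dataset seeks the primary outcome. These measures lower the risk but do not replace a stated primary estimator.

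**Conclusion.** The point holds as a gap in what the primary analysis secures. It does not show that participants will be excluded. The named t-test, taken alone, uses neither those without a six-month FJS (up to about 52 at the planned loss) nor the 6-week and 12-month scores, and the imputation clause does not settle the matter.

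The size is about 1 to 2 points of bias, or 14% to 29% of the 7-point target (1/7 and 2/7), if dropout follows early recovery differently by arm. It is close to zero if the pattern is shared. These figures rest on assumed correlations and dropout models. Neither recommended method removes bias if dropout depends on the unseen six-month score itself.

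It would be wrong to read this as a loss of planned power. The 173 per arm already allows for the missing scores, and using the other visits adds only about 1 to 3 percentage points. The change is worth making for protection against bias and for a single unambiguous primary result.

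**What to change.** In the Statistical analysis section, name one primary estimator that uses all observed FJS. Either of these would do:

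- the six-month between-arm contrast in change from a mixed model for repeated measures on FJS (arm by visit, unstructured covariance), including every randomised participant with any FJS; or
- the t-test already named, run on data multiply imputed separately by arm, with the 6-week and 12-month FJS in the imputation model, and stated to be the primary result.

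Keep the observed-case t-test as a sensitivity analysis, and align the missing-data section with the choice.

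The cost is wording and slightly more analysis work, with no new data. If the 12-month visit is included, the primary analysis must wait for it. Recruitment over 36 months plus 12 months of follow-up comes to 48 months, plus the roughly six weeks from enrolment to surgery, and the protocol places final analysis in year 5. If an earlier primary report is wanted, the model can stop at six months and still use the 6-week score.

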### **Primary outcome**

Change in Forgotten Joint Score from baseline to six months postoperatively.

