### ***Randomisation***

Participants will be randomised in a 1:1 ratio to receive either manual TKA or VELYS robot-assisted functional alignment TKA. Randomisation will be performed using a secure web-based system (Research Electronic Data Capture [REDCap], Vanderbilt University, USA) incorporating computer-generated permuted block randomisation, stratified by recruitment centre. Block sizes will be randomly varied and concealed to ensure allocation concealment. Following written informed consent and collection of baseline data, site research staff will enrol and randomise participants.

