### **Subgroup analyses**

Predefined subgroup analyses will explore potential differences in outcomes according to: age; sex; BMI; socioeconomic deprivation level; primary compartment involved (medial, lateral, or patellofemoral); CPAK group and restoration; VELYS-acquired intra-operative data (for raTKA group).

These subgroup analyses will extend the primary models by including interaction terms and will be considered exploratory. A generalised linear model will be applied, incorporating allocation group, age, site, surgeon, gender, BMI ( $\geq 35$  kg/m^2), and the primary compartment affected (medial, lateral, or patellofemoral) as covariates. Both fixed- and random-effects modelling will be employed to assess robustness. Sensitivity analyses will explore model assumptions and include both modelling approaches. Other subgroup analyses may be pre-specified as appropriate.

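### The primary t-test on change in FJS uses baseline with a fixed slope of 1 and omits centre; a baseline- and centre-adjusted linear model would be at least as powerful at the same n, and the SD of 24 needs defining

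*Protocol*

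**What the plan says.** The Protocol defines the primary outcome as "Change in Forgotten Joint Score from baseline to six months postoperatively". Its Statistical analysis section compares the arms on "change in FJS (preoperatively versus 6 months post-surgery") by intention to treat. It names the method: a Student's "independent t-test will be used to compare mean scores between groups", replaced by Welch's test if variances are unequal. No covariate is mentioned. On reporting it says: "The results will be reported as mean differences with 95% confidence intervals and p-values".

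Four other sections bear on this choice:

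- **Data collection:** FJS is among the questionnaires completed at the pre-operative visit, so baseline FJS is available.
- **Randomisation:** the system is described as "incorporating computer-generated permuted block randomisation, stratified by recruitment centre".
- **Sample size:** the calculation is based on "detecting a minimum clinically important difference (MCID) of 7 points in the FJS at six months post-operatively" and "a standard deviation of 24 points", with one-sided alpha 0.05 and 80% power. This gives 147 per group, raised to 173 for 15% loss. A blinded re-estimation of the variance follows the first 100 participants.
- **Subgroup analyses:** "These subgroup analyses will extend the primary models by including interaction terms and will be considered exploratory". The generalised linear model described there includes site and surgeon but not baseline FJS.

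**The concern.** Three things do not fit together.

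1. The variable tested is change, while the sample size is worded for the score at six months. The two have different SDs, and the section does not say which one 24 is.
2. A change score removes baseline with a slope fixed at 1. When the true regression slope differs from 1, precision is lost compared with estimating the slope. Centre, on which the randomisation is balanced, is not in the primary analysis, although site is in the exploratory subgroup model.
3. The subgroup section presupposes primary models that can take interaction terms, but the primary analysis is a two-sample test.

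At stake are the precision of the main result in a design sized with almost no slack, and which variance the blinded re-estimation should estimate.

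**Working it through.** **Inputs from the Protocol:** difference 7, SD 24, one-sided alpha 0.05, power 80%, 147 evaluable per group, 15% loss.

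**Inputs not in the Protocol (assumed ranges):** baseline SD s0 = 12 to 24; correlation r between baseline and six-month FJS = 0 to 0.5.

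**Step 1. Reproduce the plan's figure.** The normal approximation gives n = 2 × (1.645 + 0.842)² × 24² / 7² = 145.4, so 146. With the noncentral t distribution, power is 79.99% at 146 and 80.2% at 147, so the t-based answer is 147. Then 147 / 0.85 = 172.9, so 173 per group and 346 in total. The stated figures reproduce.

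**Step 2. Formulas.**

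- SD of change = √(s0² + s6² − 2·r·s0·s6), where s6 is the six-month SD.
- ANCOVA residual SD = s6·√(1 − r²).
- SD of change exceeds s6 exactly when s0² > 2·r·s0·s6, that is, when r < s0 / (2·s6).

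**Step 3. Reading A: 24 is the SD of the six-month score.** Power is from the noncentral t with 147 per group, one-sided 0.05, at r = 0.3:

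| Baseline SD | SD of change | t-test power | ANCOVA SD | ANCOVA power |
|---|---|---|---|---|
| 12 | √547.2 = 23.4 | 82% | 24·√0.91 = 22.9 | 83% |
| 16 | √601.6 = 24.5 | 79% | 22.9 | 83% |
| 20 | √688.0 = 26.2 | 74% | 22.9 | 83% |
| 24 | √806.4 = 28.4 | 68% | 22.9 | 83% |

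The grid s0 = 12, 16, 20, 24 by r = 0, 0.2, 0.3, 0.4, 0.5 has 20 cells. Across it the SD of change runs from 20.8 to 33.9 and t-test power from 55% to 89%. ANCOVA power runs from 80% to 89%. The t-test keeps 80% in 7 of the 20 cells. At s0 = 12 and r = 0.5 both SDs are 20.8 and ANCOVA gains nothing.

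**Step 4. Reading B: 24 is the SD of change.** The t-test has its planned 80%. With equal SDs the ANCOVA residual SD is 24·√((1 + r)/2). At r = 0.3 this is 19.3, giving 93% power.

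**Step 5. Why ANCOVA does not lose under either reading.** The residual SD is the smallest SD of (six-month score − b × baseline) over all slopes b. The unadjusted six-month score is b = 0 and the change score is b = 1. The residual SD therefore cannot exceed 24, whichever of the two 24 describes. Estimating one slope and the centre terms costs few degrees of freedom out of about 294 evaluable participants (2 × 147).

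**Step 6. Two-sided check.** At two-sided 5%, the level that matches a 95% interval, the unadjusted calculation with SD 24 has about 70% power at 147 per group. ANCOVA under reading A has 70% to 82% for r from 0 to 0.5.

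**Step 7. Centre.** Omitting a stratification factor that predicts outcome tends to overstate the standard error. The Protocol gives no between-centre variance, so the size cannot be computed.

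**The case against.** The strongest defence is that nothing here makes the primary result wrong. In a 1:1 randomised trial a t-test on change is unbiased, its type I error is controlled, and it matches the declared outcome. Leaving out centre errs on the conservative side. All of this stands.

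A reader might infer that the trial is underpowered. The Protocol does not establish that. It does not say that 24 is the six-month SD; if it is the SD of change, there is no shortfall. Even under reading A the shortfall depends on r and the baseline SD, neither of which is given. The 55% figure needs r = 0 together with a baseline SD as large as the six-month SD.

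The blinded re-estimation is also a real safeguard. If the SD of change proves larger than 24, that step could raise n, whereas every power figure above holds n at 147. But it would meet with extra recruits a loss that adjustment may avoid without them. It also protects the right quantity only if it estimates the variance of the analysis actually used.

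A reader might also say that baseline FJS is ignored. It is not: the change score subtracts it. What is missing is an estimated slope.

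Finally, the choice is not simply left to a later analysis plan. The Protocol names the test, so a different primary method there would contradict it.

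**Conclusion.** The point holds as a matter of efficiency and consistency. The planned test is valid but can be less precise than the data already being collected allow.

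Whether it falls short of 80% one-sided power is conditional. It does so only if 24 is the six-month SD, r is below half the ratio of baseline to six-month SD, and the re-estimation does not raise n. The case for ANCOVA does not depend on settling this, since at the same n it has at least the stated 80% one-sided power under both readings.

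It would be tempting to conclude that ANCOVA also repairs the mismatch between the one-sided alpha in the sample size and the 95% intervals in the analysis. It does not: two-sided power is about 70% to 82% under reading A for r from 0 to 0.5. That is a separate matter.

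Severity: should-fix, as a free improvement, not must-fix.

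**What to change.** 1. Make the primary analysis a linear model of six-month FJS on allocation, baseline FJS (continuous) and centre, reporting the adjusted mean difference with its interval. With baseline in the model, the allocation coefficient is the same if change is the dependent variable, so the primary outcome stays as defined.
2. Keep the t-test on change as a sensitivity analysis.
3. Name this model as the primary model that the subgroup interactions extend, so that the Subgroup analyses and Statistical analysis sections agree.
4. State in the Sample size section whether 24 is the SD of the six-month score or of change.
5. Base the blinded re-estimation on the variance of the analysis used. Under this model that is the residual variance after baseline and centre, which can be estimated without allocation.

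The cost is wording in the Protocol and the analysis plan, settled before outcome data are examined. No new data and no extra participants are needed.

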### ***Surgical efficiency and task load evaluation***

An assessment of the surgical efficiency, learning curve, physical and cognitive task load costs associated with VRAS raTKA versus mTKA will be conducted. This will include an evaluation of intraoperative timings, NASA Task Load Index (TLX) scores reported by clinicians based on their perception of surgical cases (after the first and every fifth case, including non-trial training period; i.e. after 1st case, 5th, 10th, 15th etc.), and clinician-reported questionnaires.

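### Surgical times default to an unadjusted two-sample t-test that leaves out centre and surgeon: omitting centre makes it somewhat conservative, and omitting surgeon within centre costs precision

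*Protocol*

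**What the plan says.** The Outcomes section (Fig 2) lists "Surgical time (preparation, case, tourniquet & turnaround" among the secondary measures. The Statistical analysis section names an independent-samples t-test for the primary outcome, with Welch's version if variances differ and no covariates. It then says: "Secondary outcomes will be analysed similarly, appropriate to the type and distribution of the data".

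The section on surgical efficiency and task load says "This will include an evaluation of intraoperative timings" but gives no model. Randomisation uses "computer-generated permuted block randomisation, stratified by recruitment centre"; surgeon is not a stratification factor. Site and surgeon do appear as covariates, but only in the generalised linear model under Subgroup analyses. Under Surgeons and training, every surgeon must have completed cases with both techniques before recruiting, so surgeons can be expected to operate in both arms. The Multiple testing section declares secondary outcomes exploratory, reported with unadjusted p-values and 95% CIs.

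**The concern.** Operating times plausibly differ between surgeons, and between centres with different theatre teams. A two-sample t-test puts all of that variation into its error term. Two separate consequences follow.

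- **Centre** is balanced between arms by the blocked randomisation. Differences between centres therefore barely affect the estimated difference, yet they still inflate the t-test's standard error. The test rejects too rarely and its interval is too wide.
- **Surgeon within centre** is left to chance. Surgeon differences then add real noise to the estimate, and the t-test's standard error reflects that noise correctly. The test is valid but less precise than it could be.

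Efficiency is objective 5, and the health economic section costs differences in operating time. A noisier time difference than necessary weakens the evidence on both. The information needed to reduce the noise must already be held, because the subgroup models use it.

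**Working it through.** **The plan's own figures.** No power or error rate is stated for surgical times, so only the total number of cases can be checked. The inputs are "detecting a minimum clinically important difference (MCID) of 7 points in the FJS at six months post-operatively", "a standard deviation of 24 points", one-sided alpha 0.05 and 80% power. The normal formula 2 × (1.645 + 0.842)² × (24/7)² gives about 145.4, so 146; the t-based solution is 146.03, which rounds up to the stated 147. Then 147 / 0.85 = 172.9, so 173 per group and 346 in total. This reproduces. Times are recorded at surgery, so I take all 346 as available.

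**Assumptions not in the documents.** SD 20 minutes; true difference 6 minutes; two-sided 5% (matching the 95% CIs); share r of variance between surgeons 10%, 30% or 50%; 8 or 12 surgeons in 1 or 4 centres; blocks of 4.

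**Formula check.**
- The unadjusted standard error is 20 × √(4/346) = 2.15 minutes, so the 95% half-width is 1.96 × 2.15 = 4.21 minutes.
- The standardised effect is 6 / 2.15 = 2.79, so power is Φ(2.79 − 1.96) = 80%.
- With surgeon in the model the residual SD is multiplied by √(1 − r). Half-widths become 4.00, 3.53 and 2.98 minutes for r = 10%, 30% and 50%. Power is Φ(2.79/√(1 − r) − 1.96) = 84%, 92% and 98%.
- If the randomisation balanced the whole share r (one surgeon per centre), the t-test's type I error would be 2 × [1 − Φ(1.96/√(1 − r))] = 3.9%, 1.9% and 0.6%. This is the extreme case.

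**Simulation** (6,000 null and 4,000 power runs per row; simulation error about 0.3 points on type I error and 0.6 points or less on power):

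| Layout | Surgeon share | Type I: t-test | Type I: centre in model | Type I: surgeon in model | Power: t-test | Power: surgeon in model |
|---|---|---|---|---|---|---|
| 1 centre, 8 surgeons | 10% | 4.9% | 4.9% | 4.9% | 79% | 82% |
| | 30% | 5.4% | 5.4% | 5.4% | 81% | 90% |
| | 50% | 4.9% | 4.9% | 5.0% | 82% | 98% |
| 4 centres, 2 surgeons each | 10% | 5.0% | 5.4% | 5.2% | 80% | 83% |
| | 30% | 3.4% | 4.6% | 4.7% | 82% | 91% |
| | 50% | 3.0% | 4.8% | 5.2% | 85% | 97% |
| 4 centres, 3 surgeons each | 10% | 4.3% | 4.6% | 4.6% | 80% | 82% |
| | 30% | 4.3% | 5.0% | 4.8% | 81% | 91% |
| | 50% | 3.9% | 5.2% | 5.1% | 83% | 97% |

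Two patterns separate the causes. With all surgeons in one centre the t-test stays near 5% even at a 50% share, although surgeon is ignored. With four centres it falls below 5% at the larger shares, and adding centre alone brings it back to about 5%. The conservatism therefore comes from omitting centre. The larger power gain comes from adding surgeon.

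**Variation in the robot's effect between surgeons.** A further simulation used four centres with three surgeons each, 10% of variance between centres and 20% between surgeons. The surgeon-specific effect was given a variance of 5% to 20% of the total, an SD of about 4.5 to 8.9 minutes (20 × √0.05 to 20 × √0.20). When the average effect over surgeons in general is zero, the t-test rejects in 8.6% to 19.4% of trials, and a model with fixed surgeon intercepts in 10.8% to 25.1%.

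**The case against.** **The protocol does not firmly fix a t-test.** The rule is qualified by type and distribution of the data, and a detailed SAP is still to be finalised. This stands in part. That qualifier opens the door to another test for skewed or categorical data, but it does not bring in centre or surgeon. The stated default remains unadjusted, and the efficiency section does not replace it.

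**The size rests on assumed inputs.** This stands. At a 10% share the gain is about 3 points of power, and nothing in the documents shows that the share is larger.

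**The consequences are limited.** This stands too. Secondary outcomes are exploratory, and no sample size, progression criterion or stopping rule depends on a p-value for time. The economic section does not say that it takes the t-test estimate as its input.

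**A stronger reading does not hold.** A reader might infer that ignoring the surgeon pushes the false-positive rate below 5%, or that the planned intervals are invalid. The documents do not support this, because surgeon is not a stratification factor. For surgeon differences within a centre, the unadjusted interval has the right coverage and is merely wider than it need be. The rate drops only as far as times differ between centres, and variation in the effect between surgeons can push it the other way.

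**Conclusion.** The point holds as a modest inefficiency in a stated default. The unadjusted t-test omits the stratification factor and a covariate the protocol already uses elsewhere. Omitting centre makes it somewhat conservative: about 3.0% to 4.3% in the four-centre layouts at surgeon shares of 30% and 50%, and no effect in a single centre. Omitting surgeon within centre costs power: about 80% against 83% at a 10% share, 81-82% against 91% at 30%, and 83-85% against 97% at 50%. These figures depend on the assumed SD, difference, share and layout. That surgeon adjustment gains precision when surgeons differ in speed does not depend on the layout. With exploratory outcomes, this is worth correcting but does not threaten the trial's main conclusion.

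**What to change.** State in the Statistical analysis section, or in the SAP before it is finalised, that each surgical time will be analysed in minutes by a linear model with arm, centre and surgeon. Surgeon may be fixed, or a random intercept nested in centre; fixed surgeon effects already absorb centre where each surgeon works at only one. Report the adjusted mean difference with its 95% CI, and let the costing of theatre time use the same estimate.

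Add a check of surgeon-by-arm variation, such as an interaction term or random slope with surgeon-specific differences displayed. A surgeon intercept alone does not cover a time effect that differs between surgeons.

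The cost is a few sentences and slightly more analysis work. Design and sample size are unchanged, and no new data item is needed because the subgroup models already require surgeon.
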